Higher Order Aberration and Relationship with Soft Contact Lens Modulus

IRB approved 05/13/2024

Background and Rationale:

Corneal diseases, injuries, or surgeries may induce irregular astigmatism, which cannot be corrected by spectacles alone. The standard of care for managing irregular astigmatism are non-flexible rigid gas permeable lenses, hybrid lenses, piggy-back system, or scleral lenses.¹ These lenses correct the residual higher order aberrations (HOAs) induced by irregular astigmatism. However, patients may find these lenses inconvenient, cost prohibitive, difficult to insert and remove, or difficult to adapt due to increased lens awareness. When the irregular astigmatism is mild, soft contact lens can be a viable alternative.²

Custom soft contact lenses that are designed to mask mild to moderate amount of irregular astigmatism work by two ways. One is by increasing the center thickness to mimic the non-flexing nature of the GP material.³ Another way is by increasing its asphericity to limit aberrations.^{1,4,5} Still, these lenses are not readily available; most have low oxygen permeability, and their longer replacement schedule is not ideal for patients with dry eyes.⁶ Therefore, when patients have acceptable spectacle vision with low amount of irregular astigmatism, they may want to be fit in disposable soft contact lenses readily available off the shelf. Disposable soft contact lenses also have additional benefits, such as options for daily replacement, colors or tinting, and different lens materials optimized to reduce dry eye symptoms.

The modulus of a contact lens material is a measurement of its stiffness,⁴ or the material's ability to maintain its shape and resist deformation. A contact lens with a higher modulus does not mold to the eye's anatomy as readily as a contact lens with a lower modulus. To our knowledge, no studies have evaluated the correlation between soft lens modulus and HOA changes with soft contact lens wear. Previous studies on HOA and soft contact lenses have found conflicting data on whether soft contact lens wear increase or decrease HOA,^{7–10} and the most recent study was conducted in 2010 using older technology and lens design.¹¹

The purpose of this study is to determine whether the lens modulus affects the amount of HOAs in subjects wearing soft contact lenses. OVITZ xwave is a novel aberrometer that is currently used to measure HOAs in an eye. Its data is used to manufacture scleral lenses with optics to correct HOA and improve patients' vision. In this study, we will use OVITZ xwave to measure the HOA of an eye with and without soft contact lens wear. The difference in HOA will then be evaluated for its correlation with soft lens modulus.

Specific Aim:

Determine whether there is a correlation between HOAscorrection and soft contact lens modulus

Hypothesis: Soft contact lenses with stiffer modulus are more effective in reducing HOAs compared to those with softer modulus.

Primary end point: HOA of an eye with and without soft contact lens wear

Exploratory end point: Specific HOA corrected/worsened with soft contact lens.

Study Design:

This one-visit, single-arm observational study will be conducted at the Southern College of Optometry (Memphis, TN, USA). Subjects will be recruited via emails, fliers, and word of mouth. Adults (>18 years old) who are wearing single-vision soft contact lenses will be recruited.

Inclusion Criteria:

- Willing and able to provide informed consent
- Adults > 18 years old regardless of gender, race, or ethnicity
- Habitual single vision soft CL wearer for at least 1 week in any modality.

Exclusion Criteria:

- Multifocal soft CL wear
- GP or ortho K wear in the last 3 months.
- Active eye infections and inflammations.
- Current use of ocular medication.

Materials needed:

CL cases and solution. OVITZ wave system.

Sample size:

The lens modulus and HOA distribution will be used to determine sample size. The number of subjects tentatively estimated is 100.

Methods:

This will be a prospective, single-arm clinical trial, which will be registered with ClinicalTrials.gov. Subjects who meet all study criteria will be enrolled into the study. Clinical measurement will be obtained from both eyes of each subject and testing will be performed in the below order. Testing order was designed to allow for adequate time for contact lens settling. Subjects will be randomized to two groups. One group will be asked to come to the visit wearing their habitual contact lenses for at least 2 hours on the day of the visit. The other group will be asked to refrain from CL wear the day of the visit and to come wearing habitual spectacles.

1. Subject History, Eligibility, Informed Consent: Subjects will be asked to complete a screening survey to verify that they are eligible for the study. All relevant ocular, systemic, and surgical history will be gathered via a questionnaire developed by the investigators. Non-eligible subjects will be dismissed at this time or rescheduled depending upon the reason for ineligibility. Eligible subjects will be enrolled, consented, and requested to sign a privacy document.

Group 1: (presenting wearing CLs)

2. HOA with CLs: The investigator will use OVITZ xwave system to measure the amount of HOA in both the right and the left eye. The subjects will be asked to blink immediately prior to each measurement. The measurements will be repeated 3 times for each eyes.

3. CL removal: The subject will be asked to remove their contact lens. The subjects will be asked to wait for 15 minutes while their ocular system returns to homeostasis.

4. HOA without CLs: The investigator will use OVITZ xwave system to measure the amount of HOA in both the right and the left eye. The subjects will be asked to blink immediately prior to each measurement. The measurements will be repeated 3 times for each eye.

Group 2: (presenting wearing spectacles)

2. HOA without CLs: The investigator will use OVITZ xwave system to measure the amount of HOA in both the right and the left eye. The subjects will be asked to blink immediately prior to each measurement. The measurements will be repeated 3 times for each eye.

3. CL insertion: The subject will be asked to insert their habitual contact lens. The subjects will be asked to wait for 15 minutes while their contact lenses settle.

4. HOA with CLs: The investigator will use OVITZ xwave system to measure the amount of HOA in both the right and the left eye. The subjects will be asked to blink immediately prior to each measurement. The measurements will be repeated 3 times for each eyes.

References:

- 1. Rathi, V. M., Mandathara, P. S. & Dumpati, S. Contact lens in keratoconus. in *Indian Journal of Ophthalmology* vol. 61 410–415 (2013).
- 2. Sabesan, R. et al. Vision Improvement by Correcting Higher-Order Aberrations with Customized Soft Contact Lenses in Keratoconic Eyes. (2007).
- 3. Lampa, M. *Leadership in Clinical Care Custom So Lenses for Irregular Astigmatism Contact Lens Close-Up*. https://www.reviewofoptometry.com/article/custom-soft-lenses-for-irregular-astigmatism.

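### The one named analysis, a correlation of HOA difference with habitual-lens modulus, cannot show that HOA is reduced and supports association, not that modulus 'affects' HOA

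*Protocol*

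**What the plan says.** The purpose paragraph of the protocol's Background and Rationale is worded causally: "The purpose of this study is to determine whether the lens modulus affects the amount of HOAs in subjects wearing soft contact lenses". The same paragraph names the only analysis: "The difference in HOA will then be evaluated for its correlation with soft lens modulus". It does not say which reading is subtracted from which.

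The Specific Aim is to "Determine whether there is a correlation between HOAscorrection and soft contact lens modulus". The hypothesis reads "Soft contact lenses with stiffer modulus are more effective in reducing HOAs compared to those with softer modulus". The primary end point is HOA with and without the lens, with no direction attached. The exploratory end point is "Specific HOA corrected/worsened with soft contact lens".

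On direction, the Background states: "Previous studies on HOA and soft contact lenses have found conflicting data on whether soft contact lens wear increase or decrease HOA".

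On exposure, Study Design says "This one-visit, single-arm observational study will be conducted", and Methods for Group 2 says "The subject will be asked to insert their habitual contact lens". Group 1 arrives in habitual lenses. The randomisation in Methods decides only whether a subject presents in lenses or in spectacles.

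**The concern.** Two conclusions that the protocol is set up to draw go further than its named analysis.

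First, the aim speaks of correction and the hypothesis of reduction, as if the sign of the change were known, while the Background says that it is not. A significant correlation could be reported as stiffer lenses correcting HOA when they only worsen it less. The rationale concerns patients with mild irregular astigmatism who would like an off-the-shelf soft lens, and for them these two findings mean different things.

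Second, nobody is assigned a modulus. An association between the lens a subject happens to wear and the HOA change could be reported as an effect of modulus. The word 'randomized' in Methods could encourage that reading, although it does not concern modulus.

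**Working it through.** **Inputs.** From the protocol: 100 subjects (Sample size, tentative), the named correlation, habitual lenses, and the statement that earlier data conflict on direction. The protocol gives no HOA data, alpha, power or target correlation, so the figure of 100 cannot be reproduced; it is used here only as n. All other numbers are assumptions for illustration, with one value per subject.

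**Step 1: the correlation ignores the mean.** Let D = with-lens minus no-lens HOA. For any constant c, corr(modulus, D + c) = corr(modulus, D). A small made-up example: moduli 0.3, 0.5, 0.7, 1.0, 1.2, 1.5 with D = +0.12, +0.11, +0.09, +0.07, +0.05, +0.03. HOA rises with every lens (mean 0.47/6 = +0.078), yet the correlation of modulus with reduction (-D) is +0.998.

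**Step 2: what this means with 100 subjects.** Take the correlation that 100 subjects detect with 80% power at two-sided 5% (assumed): r = tanh((1.960 + 0.842)/√97) = 0.277. With the hypothesised sign, r = -0.277, |t| = 2.85, p = 0.0053. In SD units of D, the predicted change at standardised modulus z is mean - 0.277z. The quartiles of a normal modulus distribution are at z = ±0.6745, and 0.277 × 0.6745 = 0.187. The SE there is √((1 - 0.277²)/98 × (1 + 0.6745²)) = 0.117, so the 95% half-width is 1.984 × 0.117 = 0.232. The share of the modulus distribution with a predicted rise is Φ(mean/0.277).

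| Mean change (SD) | r, p | Share with predicted rise | Lower quartile (±0.23) | Upper quartile (±0.23) |
|---|---|---|---|---|
| -0.50 | -0.277, 0.005 | 4% | -0.31 | -0.69 |
| -0.25 | same | 18% | -0.06 | -0.44 |
| 0 | same | 50% | +0.19 | -0.19 |
| +0.25 | same | 82% | +0.44 | +0.06 |
| +0.50 | same | 96% | +0.69 | +0.31 |

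The interval lies below zero at the upper quartile only if the mean change is below 0.187 - 0.232 = -0.045 SD, and at the lower quartile only if it is below -0.187 - 0.232 = -0.419 SD. With no mean change, p = 0.005 would not justify the word reduction even for the stiffer lenses.

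**Step 3: association or effect.** Suppose modulus has no effect and one third factor has correlation a with modulus and b with the change. The induced correlation is a × b, and the chance of a two-sided 5% rejection follows from Fisher's z with SE 1/√97.

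| a | b | Induced r (absolute) | Chance of significance |
|---|---|---|---|
| 0.1 | 0.2 | 0.02 | 5% |
| 0.3 | 0.3 | 0.09 | 14% |
| 0.3 | 0.5 | 0.15 | 32% |
| 0.3 | 0.6 | 0.18 | 43% |
| 0.5 | 0.5 | 0.25 | 71% |

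The factor could be no-lens HOA or another lens feature. The Background itself links center thickness and asphericity to aberration, though for custom soft lenses.

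**Step 4: does adjusting for no-lens HOA settle it?** No. Take a lens feature correlated 0.5 with modulus that shifts with-lens HOA by -0.3 per SD, with modulus and the feature both unrelated to no-lens HOA and modulus inert. The slope on modulus is 0.5 × -0.3 = -0.15 with or without the adjustment. The two slopes agree, and both are wrong.

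**The case against.** The strongest reply is that the analysis fits the hypothesis, which is comparative: stiffer against softer. A correlation is a reasonable test of that, and ignoring the mean is a property of every correlation. The primary end point is neutral on direction and collects exactly what is needed for the mean change, so harm arises only if the report leaves it out. The title speaks of a relationship, the aim of a correlation, and the design calls itself observational; the causal claim rests mainly on one verb. Model form, covariates and handling of two eyes are commonly left to an SAP, which may exist.

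Most of this stands and limits the point. The correlation does answer the comparative question. A reader might infer that the protocol overlooks worsening except in its exploratory end point; the neutral primary end point contradicts that. A reader might also infer that silence on adjustment is a fault; it is not, because an SAP may cover it. What remains is that the named analysis does not use the mean change while the aim and hypothesis are worded as correction and reduction, and that no SAP can turn a habitual lens into an assigned exposure.

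**Conclusion.** The point holds as a mismatch between the conclusions the protocol words and the one analysis it names; data collection is not at fault. Severity is minor to moderate. That the correlation is blind to the mean is algebra and needs no assumption. The size, 4% to 96% of the modulus distribution with a predicted rise at the same p-value, rests on a linear relation, a normal modulus distribution, one value per subject and an assumed r.

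Stronger readings are not supported. The documents do not show that HOA rises with soft lenses, only that earlier results conflict. Nor do they show that the correlation is confounded: they give no association between modulus and no-lens HOA or any other lens feature, so Step 3 shows only what could happen with one third factor of the assumed strength. Nor may a reader conclude that a slope adjusted for no-lens HOA would establish an effect of modulus.

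**What to change.** - Define the difference as with-lens minus no-lens HOA, so that a negative value is a reduction.
- Estimate its slope on modulus by regression, with randomised group as a covariate and allowance for two eyes per subject. Keep this slope as the single test.
- Report with it the mean change and the predicted change, each with a 95% interval, the latter at the lower and upper modulus quartile. Speak of reduction only where the interval lies below zero.
- In the purpose, replace *affects* by *is associated with*. In the aim, replace *HOAs correction* by *change in HOA*.
- A slope adjusted for no-lens HOA is at most an optional sensitivity analysis. State that its agreement with the unadjusted slope does not rule out confounding.

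The model details may sit in an SAP; the definition of the difference and the two wording changes belong in the protocol. The cost is a short amendment, about one degree of freedom and a more modest claim. No new data are needed, since both conditions are already measured three times on each eye.

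### A correlation of the HOA difference with modulus in self-selected lenses cannot be attributed to modulus while centre thickness and lens power are neither restricted nor listed for recording

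*Protocol*

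**What the plan says.** The Specific Aim is to "Determine whether there is a correlation between HOAscorrection and soft contact lens modulus", with the directional hypothesis "Soft contact lenses with stiffer modulus are more effective in reducing HOAs compared to those with softer modulus". The purpose paragraph is worded causally, as an effect of modulus on HOA, and gives the analysis as "The difference in HOA will then be evaluated for its correlation with soft lens modulus". No other lens property appears in the aim, hypothesis, endpoints or analysis.

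The Background and Rationale describes two ways in which custom soft lenses mask irregular astigmatism. On thickness: "One is by increasing the center thickness to mimic the non-flexing nature of the GP material". On shape: "Another way is by increasing its asphericity to limit aberrations". It then says of modulus: "A contact lens with a higher modulus does not mold to the eye's anatomy as readily as a contact lens with a lower modulus".

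On lenses, the Inclusion Criteria ask only for "Habitual single vision soft CL wearer for at least 1 week in any modality". The lens-related exclusions are "Multifocal soft CL wear" and recent GP or ortho-K wear. Power, thickness and design are not limited, and custom soft lenses are not excluded. Methods step 1 collects a history by questionnaire. No listed step records lens product, power or thickness. The two randomised groups differ in whether they arrive wearing lenses or spectacles, not in which lens they wear.

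**The concern.** The Background gives thickness and modulus the same kind of role: each makes a soft lens less inclined to follow the shape of the eye. Two lenses of equal modulus and different thickness share one exposure value in the planned analysis.

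That alone is not a bias. The difficulty is that lenses are chosen by subjects and their prescribers, so modulus comes bundled with other features of each product and with the wearer's prescription. Randomising the order of measurement balances none of this across modulus. If high-modulus products in the sample are also systematically thinner or thicker, or are worn at different powers, a crude correlation mixes the contributions. A positive result could then come partly from thickness, and a null result could hide a modulus effect.

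Because the study has one visit and uses lenses the subjects bring, an analysis plan cannot adjust later for lens details that were never written down.

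**Working it through.** **The plan's own figure.** The only figure is the tentative 100 subjects. It cannot be reproduced, because the protocol gives no alpha, sidedness, power or target correlation. For orientation, assume two-sided alpha 0.05, 80% power and one observation per subject. The Fisher-z formula is n = ((z_alpha + z_power)/atanh(r))² + 3. For r = 0.28 it gives ((1.960 + 0.842)/0.2877)² + 3 = 97.8, so 98. With n = 100 the detectable correlation is 0.277. I use r = 0.28 below as an example only.

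**Inputs not in the documents (all assumed).**
- On-eye stiffness is proportional to E·t³, with E the modulus and t the centre thickness.
- The HOA difference depends on log stiffness, log E + 3 log t.
- SD(log E) = sE, from 0.3 to 0.7.
- SD(log t) = st, from 0.05 to 0.3.

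Under the cubic law, two lenses of equal modulus whose thickness differs by a factor of 1.25, 1.5 or 2 differ in stiffness by a factor of 1.95, 3.4 or 8. If the dependence were linear, the factors would be 1.25, 1.5 and 2.

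**Case A: thickness independent of modulus.** The correlation with modulus equals the correlation with stiffness multiplied by λ = sE / √(sE² + 9·st²).

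| sE | st | λ | r if stiffness r = 0.28 | power at n = 100 | n for 80% |
|---|---|---|---|---|---|
| 0.7 | 0.05 | 0.98 | 0.274 | 79% | 103 |
| 0.5 | 0.05 | 0.96 | 0.268 | 77% | 107 |
| 0.3 | 0.10 | 0.71 | 0.198 | 51% | 198 |
| 0.5 | 0.30 | 0.49 | 0.136 | 27% | 423 |
| 0.3 | 0.30 | 0.32 | 0.089 | 14% | 999 |

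The slope of the HOA difference on log E is not biased in any row. Thickness only adds residual variation.

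Adjustment would restore little of the correlation. In the row sE = 0.5, st = 0.3, λ² = 0.236 and stiffness explains 0.28² = 0.0784 of the variance. Modulus explains 0.0784 × 0.236 = 0.0185, and thickness explains 0.0599. The partial correlation of modulus given thickness is √(0.0185/(1 − 0.0599)) = 0.140, against 0.136 unadjusted. Precision is therefore not the main reason to adjust.

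**Case B: log thickness correlated ρ with log modulus.** The crude slope on log E, as a multiple of the slope at fixed thickness, is 1 + 3ρ·st/sE.
- sE = 0.7, st = 0.05: 1 + 0.214ρ. For ρ = ±0.5 this is 0.89 to 1.11, which is minor.
- sE = 0.3, st = 0.10: 1 + ρ. For ρ = ±0.5 this is 0.5 to 1.5.
- sE = 0.3, st = 0.20: 1 + 2ρ. For ρ = ±0.5 this is 0 to 2, so the relation could vanish or double.
- sE = 0.3, st = 0.30: 1 + 3ρ. It changes sign once ρ falls below −0.33.

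Here ρ is also an assumption. The documents do not say whether, or in which direction, thickness and modulus are associated among the lenses that will be seen.

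**The case against.** The strongest reply is that modulus is the study's question. The title, aim and hypothesis all name it, and the Background says its correlation with HOA change has not been studied. For that question modulus is scored correctly. This stands.

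A reader might infer more in three ways, and the documents do not support any of them.
- **That the protocol contradicts itself by calling thickness the thing that makes a soft lens resist flexing.** It does not. Thickness is one of two mechanisms given for custom lenses, and modulus is credited with resisting moulding as well.
- **That modulus ranks lenses wrongly.** This holds only if the target becomes bending stiffness, which the protocol never names as its exposure.
- **That omitting thickness pulls the result toward zero.** With independent thickness the weaker correlation is the true modulus–HOA correlation in such lenses. Bias needs an association between thickness and modulus.

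It can also be said that model terms belong in an analysis plan that is not shown, and that the listed data items cannot be complete, since modulus cannot be assigned without knowing the product. Both are fair. The questionnaire may capture the product. But power is not needed to assign modulus, so nothing in the protocol ensures that it is recorded. That part is fixed at the visit.

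**Conclusion.** The point holds as one of attribution. The protocol's purpose is causal, the lenses are self-selected, and the protocol itself names thickness and asphericity as properties that change masking, yet it neither restricts them nor lists them for recording. A crude correlation with modulus therefore cannot be attributed to modulus if thickness or power differs systematically between high- and low-modulus products.

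The size cannot be settled from the documents. With independence there is no bias in the slope, and the correlation is multiplied by about 0.98 to 0.32 over the assumed spreads. With association, the distortion runs from negligible to a change of sign. All of this rests on the assumed cubic stiffness law and the assumed spreads, and the association case also on an assumed ρ. This is a worthwhile and cheap improvement. It does not make the stated aim or its exposure invalid.

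**What to change.** - **Methods step 1:** record the lens product and lens power for each eye, from the pack or prescription, and take nominal centre thickness from manufacturers' data.
- **Analysis:** keep modulus as the exposure. Report the unadjusted correlation, and beside it the relation of modulus to the HOA difference with log nominal centre thickness in the model.
- **Optional, supportive only:** repeat the analysis with modulus times thickness cubed as the exposure.
- **Interpretation:** state that asphericity and other design features remain unadjusted, so even the adjusted estimate does not isolate modulus fully.

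The cost is two recorded items per eye, a look-up table and one model term. Thickness may be published at a single reference power only, so some values will be approximate and adjustment incomplete. If thickness and modulus are strongly associated, collinearity will widen the interval for modulus. That wider interval would show that the sample cannot separate the two, which the crude correlation would hide.

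### Does giving the randomised lens-wear instruction before the visit, with consent and screening listed as step 1 of the testing order, compromise the comparison?

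*Protocol*

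**What the plan says.** Study Design calls this "This one-visit, single-arm observational study". Methods puts enrolment before allocation: "Subjects who meet all study criteria will be enrolled into the study", and a few sentences later "Subjects will be randomized to two groups". The groups differ in how subjects arrive. "One group will be asked to come to the visit wearing their habitual contact lenses for at least 2 hours" on the day, while "The other group will be asked to refrain from CL wear the day of the visit and to come wearing habitual spectacles".

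The numbered testing order then opens with history, eligibility and consent. In that step, "Non-eligible subjects will be dismissed at this time or rescheduled depending upon the reason for ineligibility", and "Eligible subjects will be enrolled, consented, and requested to sign a privacy document". Steps 2 to 4 follow by group, with subjects already in lenses or spectacles.

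The Protocol does not say where or when step 1 takes place, and it describes no earlier screening or consent contact. It also gives no allocation ratio and does not say whether a rescheduled subject keeps the assigned group. The sample size is a tentative 100.

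**The concern.** The instruction governs what the subject does on the morning of the visit, so the group must be known before arrival. If step 1 happens at the visit, the order is: recruit, allocate and instruct, arrive, check eligibility, consent. People would then be randomised, and asked to change their lens wear, before agreeing to take part and before anyone knew that they qualified. Dismissals, reschedulings and non-attendance would all fall after allocation.

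In a parallel-group trial this would be serious, because the groups analysed would no longer be the groups randomised. The worry sharpens here because the two instructions ask different things of people. Group 2 is to arrive in spectacles, and no inclusion criterion requires owning a usable pair. If those who cannot comply differ in lens type or refractive error, the groups could become unbalanced on features related to HOA.

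**Working it through.** **1. The sequence.** Three statements cannot all be taken literally: there is one visit, the group decides the state on arrival, and screening and consent open the testing order. The link that makes this a contradiction is inferred, namely that step 1 happens on site. A screening survey and a history questionnaire can be completed when the visit is booked. Methods itself puts meeting the criteria and enrolment before randomisation, which is the usual order. A site wishing to follow every sentence would screen and consent at booking, allocate, instruct, and confirm at the visit.

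**2. What randomisation protects.** The Specific Aim is a correlation between HOA correction and lens modulus. The primary end point compares the same eye with its lens in and with it out, so each subject supplies both measurements. Modulus comes with the habitual lens and is not assigned. No aim, hypothesis or end point contrasts Group 1 with Group 2. Allocation sets only measurement order and wear time: at least 2 hours before the lens measurement in Group 1, and 15 minutes of settling in Group 2.

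**3. How post-allocation loss could reach the result.** Write the within-eye change as

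d = α + β·M + γ·G + error,

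with M the modulus in units of its SD among subjects analysed and G = 1 for Group 2. If G is left out, the slope on M is off by γ·Cov(G, M), because Var(M) = 1. Two things must both hold for a bias: the group must affect the change (γ ≠ 0), and losses must tie group to modulus. Unequal losses unrelated to modulus leave the slope alone. If G is in the model, the γ·Cov(G, M) term disappears.

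**4. Size under an adverse assumption.** The Protocol gives no loss rate and no allocation ratio. Assume 50 per group with equal mean modulus at the start, and a loss of 10% to 20% from Group 2 only, so k = 5 to 10. Let those lost lie a SDs from the mean of their group.

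- Shift in the Group 2 mean: k·a/(50 − k), which is 5a/45 = 0.11a and 10a/40 = 0.25a.
- Fraction in Group 2: p = (50 − k)/(100 − k), so Cov(G, M) has size p(1 − p)·k·a/(50 − k) = 50·k·a/(100 − k)².
- k = 5: 250a/9025 = 0.028a.
- k = 10: 500a/8100 = 0.062a.

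The unadjusted slope, per SD of modulus, therefore moves by about 0.03 to 0.06 of γ for each SD by which those lost differ. For scale, chance alone in an intact 50:50 randomisation gives a difference in mean modulus with SD √(1/50 + 1/50) = 0.20. The shift of 0.11a to 0.25a is of that order when a is near 1. The comparison is of size only, since the standard error reflects chance imbalance but not selective loss.

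**5. Whether the losses are selective.** Age, multifocal wear, GP or ortho-K wear in the last 3 months, and ocular medication are facts that exist before allocation and are unaffected by it. Removing such subjects afterwards does not in itself bias the groups. No measurement is made through spectacles; for Group 2 what matters is no lens wear that day. Nothing in the Protocol says that a subject who arrives without spectacles is excluded or switched.

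**6. What moving consent would gain.** The group must be known before arrival under any ordering, so non-attendance and failure to follow the instruction still occur after allocation. Earlier consent would remove only the ineligible and unwilling from the post-allocation losses, and most of the ineligibility is of the harmless kind in point 5.

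**The case for a change.** The strongest reply is that the Protocol needs a sentence on either reading. If consent is taken at the visit, a study-specific instruction precedes it; if it is taken remotely, the text does not say so. The timing of consent, eligibility and allocation belongs in a protocol and cannot be left to a statistical analysis plan. The single visit, the numbered order, and the reference to people being dismissed or rescheduled all favour the on-site reading. The sequences are also not interchangeable in wear time, and randomisation is the only stated protection against sequence lining up with lens type. Because wearers of any modality are admitted, a lens-free day may be a real change for some, so compliance could depend on lens type.

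Most of this stands as description. The timing is unstated, and the order of consent is a proper question for those who oversee the conduct of the study. What does not stand is the step from there to a damaged result. The route to bias needs a group effect on the within-eye change and also losses that depend on modulus, and the Protocol supports neither. Requiring usable spectacles would narrow who is enrolled, by leaving out wearers who rely wholly on lenses, for a benefit that the document gives no reason to expect.

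**Conclusion.** The sequence is loosely written, and the passages on the visit instruction and on step 1 do not fit together if step 1 takes place on site. It is a gap in operational wording that staff can fill sensibly by screening and consenting at booking. Saying so, and saying whether a rescheduled subject keeps the group, would be a useful clarification. It is not a defect in the design or analysis, and no change to the plan follows.

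The conclusion rests on three features of the Protocol: the end point is a within-eye change, modulus is not randomised, and no aim compares the groups. It would need revisiting if the order groups became a comparison of interest, or if losses proved large, one-sided and related to modulus. The calculated range depends on assumed equal groups of 50 and an assumed one-sided loss; neither figure comes from the Protocol.
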